6.3 Stopping rules

Adverse events defined as serious will be i) death and ii) ionised hypercalemia >1.6 mmol/L or hypercalcaemia requiring hospitalisation. All serious adverse events (SAE) will be reported to the chair of the DSMC. It is expected that death may occur during the 6 month treatment and follow up period in up to 5% of patients enrolled in the study related to TB itself (eg advanced/disseminated disease) or comorbidities (eg AIDS). An interim analysis will be performed after 25 and 50% of participants have

been followed to 2 months, or as requested by the DSMC in the event of SAE related to study drugs. The DSMC will be able to recommend that enrolment into the study ceases if they believe there is evidence that individuals are being harmed through their participation in the study. Early termination of the study (or of one of the study arms) may also be recommended if there is strong evidence of benefit or harm associated with either of the interventions at the interim analysis (p<0.01) or if there is strong evidence that further enrolment will not provide any useful information.

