9.5 Adverse events related to the study or to TB treatment

Research team members at the TB clinic and at RSMM will report all potential adverse events to the treating doctor and the local investigators ([name] and [name]) immediately. Presumed TB medication side effects will be reported to the treating physician as soon as possible, the strategy outlined in Appendix 5 should be followed, and if necessary, an Adverse Drug Reaction form completed by the treating doctor (Appendix 6). These will be reviewed by [name] and [name]. Any serious adverse effects will be reported immediately to the principal investigators and the chair of the Data and Safety Monitoring Committee.

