Appendix 5: Recognition of Adverse Events

Management of Adverse Events

Definitions

Adverse Event (AE): any untoward medical occurrence in a clinical trial subject administered a pharmaceutical product, not necessarily related to the study drugs or TB drugs. FILL IN ADVERSE EVENTS REPOTING FORM and record on patient's weekly data collection form and medical file. Report to [name] and [name] [name] as per Safety Reporting Flwoshart.

Serious adverse event (SAE): any untoward medical occurrence in a clinical trial subject administered a pharmaceutical product, which is life-threatening, results in death, requires hospitalisation or prolongation of existing hospitalisation, results in significant disability / incapacity or congenital anomaly / birth defect. FILL IN SERIOUS ADVERSE EVENTS REPOTING FORM and record on patient's weekly data collection form and medical file. Report to [name] and [name] [name] as per Safety Reporting Flwoshart.

Potential study drug-related AE

Arginine

- Diarrhoea
- Bloating
- Nausea
- Vomiting
- Mild to moderate abdominal pain
- Urticarial skin rash

Vitamin D

- Asymptomatic hypercalcaemia defined as $iCa^{2+} > 1.32 \text{ mmol/L}$
- Symptomatic hypercalcaemia i.e. $iCa^{2+} > 1.32$ mmol/L with one or more of the following symptoms or signs:
 - o Gastrointestinal: Nausea, Vomiting, Abdominal pain, Constipation, Anorexia
 - Neurological / Psychiatric: Fatigue, Irritability, Confusion, somnolence, Coma
 - Renal: Polyuria, dehydration
 - Others: Bone pain, itch.

Syndromic management of adverse events adapted from (1)

Side effect	Study drug most likely to be	TB drug most likely to be	Perform liver function	Perform serum ionised	Management		
	responsible	responsible	tests	calcium			
					Hypercalcaemia	Abnormal LFTs identified	No biochem. abnormality
Minor							
Mild to moderate anorexia, nausea, abdominal pain, bloating	Either L-arginine or vitamin D	Rifampicin > isoniazid	Yes	Yes	Withdraw patient from study, manage hypercalcaemia in standard fashion ¹	Follow standard protocol (monitor closely; consider H and R cessation if LFT elevation >5x normal)	Advise taking medications with meals
Mild to moderate diarrhoea	arginine	Rifampicin > isoniazid	Yes	No		As above	No change required unless diarrhoea is severe and persistent
Constipation	vitamin D	none	No	Yes			Standard treatment
Joint pains	neither	pyrazinamide	No	No	Give aspirin or NSAID		
Burning sensation in feet	neither	isoniazid	No	No	Give pyridoxine 50-75mg daily		

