- If iCa > 1.32 mmol/L at any reading during treatment, follow the flow chart below.
- Hospitalization should be avoided where possible (IV saline can be given in the TB clinic or outpatient clinic); requirement for hospitalisiation in severe, symptomatic people will be discussed on a case-by-case basis.

Hypercalcaemia Grade	Ionised calcium	Equivalent total calcium level (=iCax2)
Mild	1.32 – 1.39 mmol/L	2.60 – 2.79 mmol/L
Moderate	1.40 – 1.49 mmol/L	2.80 – 2.99 mmol/L
Severe, potentially symptomatic	1.50 – 2.25 mmol/L	3.00 – 4.49 mmol/L
Very severe	> 2.25 mmol/L	> 4.50 mmol/L

Symptomatic hypercalacaemia will be defined as one or more of the following symptoms or signs occurring in a person with ionised

calcium > 1.5 mmol/L

- 1.1.1.1 Gastrointestinal: Nausea, Vomiting, Abdominal pain, Constipation, Anorexia
- 1.1.1.2 Neurological / Psychiatric: Fatigue, Irritability, Confusion, somnolence, Coma
- 1.1.1.3 Renal: Polyuria, dehydration
- 1.1.1.4 Others: Bone pain, itch.

Adverse Events Reporting Form

(Non-Serious)

[figure not shown]

If any adverse experiences (including intercurrent illnesses) occurred between this visit and the previous visit, complete this page including your signature. If no adverse experiences occurred, check "None". Sign and date this page at lower right.

None 🗌

Description of Event Onset Date	Onset Date	End Date	Ongoing?	Duration	Туре	Severity	Was the vent serious?	Relationship to Study Drug*	Effect on Test Drug	Outcome of Event	Treatment Required
If the event can be defined as a syndrome rather than a grouping of individual symptoms, please list as a syndrome.	dd/mm/yy	dd/mm/yy	0 = No 1 = Yes	Complete only if duration is less than 24 hours	1 = Single Occurrence 2 = Intermittent 3 = Continuous	1 = Mild 2 = Moderate 3 = Severe	0 = No 1 = Yes	0 = None (disease related) 1 = None (intercurrent illness) 2 = Unlikely (remote) 3 = Possible 4 = Probable 5 = Related	0 = None 1 = Reduced 2 = Interrupted 3 = Discontinued	0 = Recovered 1 = Improved with residual effects 2 = Remained the same 3 = Worsened 4 = Unknown	0 = None 1 = Medication 2 = Hospitalisation 3 = Other

Complete the Serious Adverse Experience / Withdrawal Report Form and notify [Sponsor] immediately. 2Enter in the Concomitant Medications Form

BALKIL HUSP	Serious Adverse Events Reporting Form
Report Date:	Report Type: Initial E Follow-up
Study Drug(s):	UNKOWN: Blinded study Investigator Name:
Site:	TB Clinic RSMM Puskesmas

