Subject Information: Number:	TAD- Name: Date of Birth: Gender: M F
Serious Adverse Event Descr	ption:
SAE Start Date:	
	Check applicable category(ies) for the SAE:
	Fatal Congenital anomaly/Birth defect
	Life-threatening Intervention to prevent any of the other
	Caused or prolonged in-patient hospitalization
	Significant or permanent disability
Was the subject withdrawn from	m the study due to the SAE? Yes No
Maximum Intensity:	Mild Moderate Severe
Outcome:	Resolved Ongoing Death Unknown

NIHRD-MSHR Health Research Collaboration ADAPT study

Study HREC Number 07/40

TAD- |__|_|_|_

Outcome Date: 20_	
	Causal relationship to study drug (Check one)*:
	None Probable
	Unlikely (Remote) Highly Probable
	Possible Unknown
Study Drug Information:	
1	Oral L-arginine / placebo Total Daily Dose:
	Most Recent Stop Treatment Start Date: 20 Date: 20 duration: weeks days
	Drug Stopped Due to AE? Yes 🗌 No 🗌 N/A
	Dose Change Due to AE? None
	If Stopped or Suspended, was subject rechallenged? Yes I No No N/A
	If Yes, Date of Rechallenge: 20 Did AE reappear after rechallenge? Yes No No N/A
2	Oral vitamin D / placebo Total Daily Dose:
	Most Recent Stop Treatment Start Date: _ 20 Date: _ 20 duration: weeks days
	Drug Stopped Due to AE? Yes No No N/A
	Dose Change Due to AE? None C Reduced Suspended C
	If Stopped or Suspended, was subject rechallenged? Yes I No No N/A
	If Yes, Date of Rechallenge: 20

NIHRD-MSHR Healt	h Research	Collaboration	ADAPT	study
------------------	------------	---------------	-------	-------

Study HREC Number 07/40						TAD-
Did AE reappear after rechallenge?		Yes		No 🗌	N/A	
Has Investigator unblinded treatmen	nt?	Yes		No 🗌	N/A	
If Yes, Date of Unbline	ding:	20	_			
Subject Treatment arr		tive ug 🗌		Placebo		
Concomitant Medications:						
Drug Name	Indication	Start date		Dose	Stop Date	

Narrative: Other Relevant History:

Investigator Signature

Date

*Relatedness of Adverse Event to an Intervention

Unrelated

Adverse event is clearly due to extraneous causes (e.g., underlying disease, environment)

Unlikely (must have 2)

Does not have temporal relationship to intervention.

- 1. Could readily have been produced by the subject's clinical state.
- 2. Could have been due to environmental or other interventions.
- 3. Does not follow known pattern of response to intervention.
- 4. Does not reappear or worsen with reintroduction of intervention.

Possible (must have 2)

- 1. Has a reasonable temporal relationship to intervention.

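### Serious adverse event is defined four different ways, and the section 6.3 version does not match Appendix 6's own hypercalcaemia grades, so expedited reporting to the DSMC is inconsistent

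*Protocol*

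**What the plan says.** All places are in the protocol.

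- **Section 6.3 (Stopping rules)** gives a closed list: "Adverse events defined as serious will be i) death and ii) ionised hypercalemia >1.6 mmol/L or hypercalcaemia requiring hospitalisation". It continues: "All serious adverse events (SAE) will be reported to the chair of the DSMC". The same section lets the DSMC ask for an additional interim analysis when an SAE is related to a study drug.
- **Section 9.5**: "Any serious adverse effects will be reported immediately to the principal investigators and the chair of the Data and Safety Monitoring Committee". It does not say which definition of serious applies.
- **Appendix 5** defines an SAE as an untoward occurrence "which is life-threatening, results in death, requires hospitalisation or prolongation of existing hospitalisation, results in significant disability / incapacity", and also names birth defects. It sets no calcium level.
- **Appendix 6, 'Serious' list**: death, a life-threatening condition, hospitalisation. It sets no calcium level.
- **Appendix 6, SAE reporting form**: categories similar to those of Appendix 5, plus "Intervention to prevent any of the other" (the wording breaks off in the available text).
- **Appendix 6, grade table**: ionised calcium of "1.50 – 2.25 mmol/L" is labelled "Severe, potentially symptomatic".
- **Appendix 6, hypercalcaemia instructions**: "Hospitalization should be avoided where possible (IV saline can be given in the TB clinic or outpatient clinic". The need to admit severe, symptomatic people is left to individual discussion.
- **Symptomatic hypercalcaemia** is calcium above 1.32 mmol/L with symptoms in Appendix 5 and in the Appendix 6 list of expected effects. Under the Appendix 6 grade table it is calcium above 1.5 mmol/L with symptoms.

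**The concern.** Hypercalcaemia is the harm of vitamin D that the protocol itself singles out (section 6.1). Whether a case is called serious decides two things: whether the DSMC chair gets an expedited notice, and whether the committee's option of an unscheduled interim analysis comes into play. If the definition changes from section to section, staff following different pages of the same protocol will report the same event differently. A count of SAEs built that way partly reflects which page was followed and whether the participant was admitted, as well as how much toxicity occurred.

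The mismatch with the grade table adds to this. Section 9.6 gives the committee power to stop the study at once for severe adverse events attributable to study medication. Yet section 6.3 does not require every event that Appendix 6 grades as severe to be sent to it.

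**Working it through.** There is no sample size or power figure to reproduce. The check sets the definitions side by side, with one piece of interval arithmetic.

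**Step 1. The gap on calcium level.** Inputs: the 6.3 threshold of above 1.6 mmol/L, and the Appendix 6 'Severe' band of 1.50 to 2.25 mmol/L.

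- Width of the band: 2.25 − 1.50 = 0.75 mmol/L.
- Part of the band not above the 6.3 threshold: 1.60 − 1.50 = 0.10 mmol/L.
- Share of the width: 0.10 / 0.75 = 0.133, or 13%. The other 0.65 / 0.75 = 87%, and the whole 'Very severe' grade, are serious under 6.3 on calcium alone.
- By the table's own conversion (total = 2 × ionised), the gap is a total calcium of 3.00 to 3.20 mmol/L.

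These are shares of a measurement range. The protocol does not say how many participants would fall in it.

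**Step 2. The same event under each definition.**

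| Event | 6.3 | Appendix 5 | Appendix 6 'Serious' list | SAE form |
|---|---|---|---|---|
| Calcium 1.50–1.60, treated in clinic, not admitted ('Severe') | No | Only if judged life-threatening or disabling | Only if judged life-threatening | Possibly, through the intervention category |
| Calcium above 1.60, treated in clinic, not admitted | Yes | Only if judged life-threatening or disabling | Only if judged life-threatening | Possibly, through the intervention category |
| Calcium 1.40–1.49, admitted for it ('Moderate') | Yes | Yes | Yes | Yes |
| Admission for a cause other than hypercalcaemia | No | Yes | Yes | Yes |

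Only the third row gives one answer throughout. The disagreement runs in both directions: 6.3 is narrower than the appendices on non-calcium events and wider on calcium above 1.60 mmol/L.

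**Step 3. The hospitalisation limb.** In the first row, the only other way to become serious under 6.3 is a need for hospitalisation. Appendix 6 says to avoid admission where possible and that intravenous saline can be given in the clinic. So two participants with the same calcium and symptoms can differ in reportability because one was admitted.

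**Step 4. Symptomatic hypercalcaemia.** A participant with symptoms and calcium in the 'Moderate' range (1.40 to 1.49 mmol/L) is symptomatic under Appendix 5 and the expected-effects list, but not under the text below the grade table. Appendix 6 contains both versions.

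**The case against.** The other side has good points.

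- **Seriousness and severity are different scales.** A severity grade need not share its cut-off with a reporting threshold, so 1.50 against 1.6 is not by itself a contradiction. This stands. What it does not answer is that the definitions of serious also disagree with each other.
- **There are other routes.** A reader of 6.3 might infer that its list is the only non-fatal trigger. The document does not support that: Appendix 5, the Appendix 6 list and the SAE form add further non-fatal categories, and section 9.5 sends any serious adverse effect to the DSMC chair.
- **Most of the 'Severe' band is covered.** A reader might infer that severe vitamin D toxicity can bypass the committee altogether. Under 6.3, anything above 1.6 mmol/L is reportable wherever it is treated. Below that, what is missing is a required SAE report; the committee may still see the case at its two scheduled reviews.
- **The hospitalisation limb is weakened, not removed.** Appendix 6 leaves admission of severe, symptomatic people to case-by-case discussion. Nor does any section set different admission rules for clinic and hospital, so a claim that reporting follows site policy goes too far.
- **Two flow charts cannot be seen.** Appendix 5 refers to a safety reporting chart and Appendix 6 to a hypercalcaemia chart. A reporting step there cannot be excluded, though it would not reconcile the written definitions.
- **Other safeguards exist.** Symptoms attributed to vitamin D or hypercalcaemia go at once to the investigators (section 3.3.3.4), and further vitamin D or placebo is withheld when calcium is raised (section 6.1). These protect the participant but do not inform the committee.

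**Conclusion.** The point holds as a conflict of definitions. Section 6.3, Appendix 5, the Appendix 6 'Serious' list and the SAE form do not agree on what is serious, and symptomatic hypercalcaemia is defined two ways. Under 6.3 taken alone, an event at 1.50 to 1.60 mmol/L managed without admission is 'Severe' yet needs no SAE report. Above 1.60 mmol/L without admission, 6.3 requires a report and the other definitions do not clearly do so.

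The number of events affected is probably small, because section 6.1 expects the risk of symptomatic hypercalcaemia to be very low; the protocol gives no figure from which to estimate it. Correction is still worthwhile, because the definition governs expedited notice to the committee and its option of an unscheduled interim analysis. The conclusion rests on the text as available, without the flow charts. It takes no position on which calcium level or management rule is right.

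**What to change.** Reconcile section 6.3, Appendix 5, the Appendix 6 'Serious' list, the grade table with its symptomatic definition, and the SAE form. Write one definition of a DSMC-notifiable hypercalcaemia event and use it in 6.3, 9.5, both appendices and the form. It should not depend on where care is given. Settle on one definition of symptomatic hypercalcaemia, and make 6.3 agree with the appendices on serious events other than hypercalcaemia. Bring the two flow charts into line. The sponsor chooses the threshold.

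The cost is wording in these places and a few more notices to the DSMC chair. Treatment, tests, visits and staffing do not change.

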5 STATISTICAL ANALYSES

5.1 Sample size

Sample size has been calculated using the graphical method for 2x2 factorial designs informed by the Fleiss equation, described by Byth and Gebski (71). Making a conservative assumption of sub-additive interaction between the 2 interventions (interaction coefficient of 0.5), then at a level of significance of 5%, a sample size of 444 (111 participants in each arm) will provide 82% power to demonstrate that each treatment results in a 20% reduction in the proportion culture positive at one month (from 60% to 40%), assuming loss to follow up of 10%. As there have been no trials of co-administration of vitamin D and L-arginine, the characteristics of potential immunological interactions can be extrapolated only from in vitro macrophage studies, in which findings conflict: vitamin D was found to inhibit iNOS expression in one study(44); yet upregulate NOS2A in another (68); the latter study also found the suppressive effect of vitamin D on MTB replication to be partially impaired if NO formation was inhibited. Including a sub-additive interaction term in the sample size calculation provides a margin a caution; if there is minimal or no interaction between the two interventions, our power will be greater. A factorial design rather than a three-arm study allows us to investigate whether if is safe and effective to co-administer the two interventions. Acknowledging the possibility of statistical interaction between the terms, we have an *a priori* plan to analyse primary and secondary outcomes according to subgroups receiving single interventions as well as according to the overall factorial model (71).

Mean time to culture negativity in mostly drug sensitive TB is 32 days (New York) (72) -57 days (Turkey) (73). Based on bacillary burden and extent of cavitatory disease, we estimate a minimum of 60% of Timika patients will be culture positive at 1 month. Our power will be increased if this proportion is higher. This sample size will also be powered to detect a 9% absolute difference in the mean improvement in percent predicted FEV1, a component of the composite endpoint, at 6 months. Mean baseline percent predicted FEV1 in Timika is 63.6% predicted (SD 22) rising to 77.9% predicted (SD 23) at 6 months. Each month, at least 25 eligible smear positive pulmonary TB patients are diagnosed and treated at the Timika study site. If 90% agree to be enrolled, recruitment will take <2yrs to complete.

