5.2 Outcome Analysis

The primary analysis of all outcomes will be by intention to treat. All participants in the study will contribute outcomes for analysis whenever possible. Each participant's success or failure for the primary outcome will be determined by an independent observer who will be blinded to the intervention. Analyses will use Intercooled Stata 9.2 (Stata Corp, College Station, Texas, USA). 95% confidence intervals and/or p values <0.05 will be employed to signify statistical significance.

As per recent clinical journal requirements, ADAPT will be registered with the protocol registration system at Clinicaltrials.gov.

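### Two interim looks that may stop at p<0.01, then an unadjusted final p<0.05, give about 6.1% error per test instead of 5%, and the rule names neither the outcome nor the model it tests

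*Protocol*

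**What the plan says.** Section 6.3 sets the interim schedule: "An interim analysis will be performed after 25 and 50% of participants have" been followed to 2 months. Further looks are possible at the committee's request after serious events related to study drug. Early termination of the study or of an arm may be recommended "if there is strong evidence of benefit or harm associated with either of the interventions at the interim analysis (p<0.01"). No outcome or model is attached to that p-value.

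Section 5.2 gives the final criterion: "95% confidence intervals and/or p values <0.05 will be employed to signify statistical significance". It makes no allowance for the looks.

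Section 5.1 states the design: "at a level of significance of 5%, a sample size of 444 (111 participants in each arm) will provide 82% power" for each treatment, for a fall from 60% to 40% culture positive at one month with 10% loss to follow-up. It adds: "Making a conservative assumption of sub-additive interaction between the 2 interventions (interaction coefficient of 0.5"). The same section announces an a priori "plan to analyse primary and secondary outcomes according to subgroups receiving single interventions as well as according to the overall factorial model", and neither analysis is said to decide. Section 4.1 lists two primary outcomes: culture at 1 month and a clinical composite at 2 months.

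**The concern.** A trial that may stop early on a significance threshold has already used part of its error allowance when it reaches the final analysis. Testing there at the full 0.05 takes the total above the level the protocol states.

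The rule is also incomplete. A monitoring committee reading Section 6.3 cannot tell which outcome triggers it, or whether the p-value comes from the factorial comparison or from one single-drug arm against double placebo. At the end, with neither model ranked first, the deciding analysis could be chosen after the results are known.

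An early crossing also needs a large observed difference, so a stop for benefit at the first look would report an effect larger than the one planned for.

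**Working it through.** **Inputs.** From 5.1: 444 participants, 111 per arm, 5% level (taken as two-sided), 60% v 40%, 10% loss, interaction coefficient 0.5. From 6.3: looks at 25% and 50%, p<0.01. From 5.2: final p<0.05. Information is taken as proportional to participants.

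**The plan's own figure.** Evaluable per arm: 111 × 0.9 ≈ 100. The stated 82% is reproduced to within a point in two ways:
- single drug against double placebo, 60% v 40%, 100 per group, no continuity correction: 81.2%;
- factorial margin, about 200 per group, interaction on the log-odds scale, continuity-corrected: 81.7%.

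So the 82% does not show which analysis was meant to be primary.

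**Error of the stopping rule, one test.** Under the null, the test statistics at information 0.25, 0.5 and 1 are jointly normal with correlation √(tᵢ/tⱼ), that is 0.707, 0.5 and 0.707.
- P(|Z₁|>2.576 or |Z₂|>2.576 or |Z₃|>1.960) = 6.08%.
- Spent at the two looks: 1.77%, of which about 0.9% is in the benefit direction.
- Overall error in the benefit direction: 3.04% instead of 2.5%.
- One assumed unscheduled look at 75%, also at p<0.01: 6.19%.

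**The two models estimate different effects.** Single drug: 60% v 40%, odds ratio (0.4/0.6)/(0.6/0.4) = 0.444. If the second drug adds half the effect on the log-odds scale, the combination odds are 0.667 × √0.444 = 0.444, or 30.8%.
- Margin without the drug: (60 + 40)/2 = 50.0%.
- Margin with the drug: (40 + 30.8)/2 = 35.4%.
- Difference: 14.6 points, against 20 for the single-drug contrast. Halving on the risk-difference scale gives a 30% combination cell and 50% v 35%, so the contrast does not hinge on the scale.

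**What p<0.01 requires at the 25% look.** Evaluable per margin: 444 × 0.25 × 0.9 / 2 ≈ 50. The mean rate is (0.500 + 0.354)/2 = 0.427. The standard error is √(2 × 0.427 × 0.573 / 50) = 0.099. The required difference is 2.576 × 0.099 = 25.5 points, against 14.6 planned.

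**Ways to restore 5%.**

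| Looks | Final level | Overall error |
|---|---|---|
| p<0.01 | 0.05 | 6.08% |
| p<0.001 | 0.05 | 5.08% |
| p<0.001 | 0.049 | 5.0% |
| p<0.01 | 0.038 | 5.0% |

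Power for the planned margin effect (continuity-corrected, counting early stops) is 82.3% under the present rule and 81.5% with 0.001/0.049. Keeping p<0.01 and lowering the final level to 0.038 costs about 3 points. For the single-drug contrast, ignoring early stops, power goes from 81.2% to 78.0%.

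**The case against.** Several points on the other side stand.

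- **The rule is advisory.** Section 6.3 says termination may be recommended. If the trial never stops for benefit, the per-test error returns to 5%. The 6.1% is conditional on a crossing being acted on and claimed.
- **The looks add only about one point per test.** A reader might multiply over two drugs and two outcomes and infer a 22% chance of some false positive: 1 − (1 − 0.0608)⁴ = 22.2%. The documents do not support that as the size of this problem. Section 5.1 sets 5% for each treatment, separate tests of two different drugs are defensible, and 1 − 0.95⁴ = 18.5% would arise with no looks at all. Applying p<0.01 to both primary outcomes is itself a reading, since 6.3 names none.
- **The 1.8% is not all false benefit.** It counts crossings towards harm as well.
- **A power gap between the models is not established.** A reader might infer that the single-drug contrast has only 77% power against the stated 82%. That needs a continuity correction and an interaction scale that 5.1 does not give. Without the correction the single-drug figure is 81.2%.
- **Loss of the 6-month outcomes does not follow.** Section 6.3 speaks of ceasing enrolment or terminating the study or an arm. It does not say that follow-up of those already enrolled would end.

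A statistical analysis plan, not shown here, might name the primary model. It could not lower the final level without contradicting Section 5.2, and the thresholds fixed in the protocol do not hold 5% together.

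**Conclusion.** The point holds at modest size. As written, one drug tested on one outcome with one model carries about 6.1% two-sided error, not 5%. This assumes two-sided tests, information proportional to participants, and a crossing that leads to a stop and a positive claim.

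Two omissions make it worse: Section 6.3 does not say what is tested, and Section 5.1 does not say which of two analyses with different target effects decides. A stop for benefit at the 25% look would rest on an observed difference of about 25 points, well above the planned margin effect of about 15.

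Within one drug, two primary outcomes each tested at 0.05 raise the error further, to at most about 1 − 0.95² = 9.75% before any looks if they are independent, and less if they are correlated. That is separate from the stopping rule. Severity: should-fix, before any unblinded look.

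**What to change.** **Section 6.3.** Set stopping for benefit at p<0.001 at both looks and test the final analysis at 0.049. Alternatively, keep p<0.01 and test the final analysis at about 0.038. Leave harm to the monitoring committee's judgement. State that the benefit rule applies to 1-month culture in the factorial comparison.

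**Sections 5.1 and 5.2.** Name the factorial at-the-margin comparison as the primary analysis for each drug, adjusted for the other drug and for the two stratification factors in Section 7 (place of diagnosis and ethnicity). Report the single-intervention contrasts and the interaction estimate as supportive. Replace the 0.05 in 5.2 with the final level chosen.

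**Left to the sponsor.** A hierarchy or a split of the 5% would each deal with the two primary outcomes. Each changes what the trial may claim, so the choice should be stated but is not prescribed here.

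**Cost.** Protocol and monitoring-committee wording, with no extra participants. With 0.001/0.049 power falls by under one point and early stopping for benefit becomes rarer. With 0.01/0.038 power falls by about 3 points.
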